**Study Procedures:**

Overall, study procedures include (a) pre-screening for initial eligibility determination; (b) clinical interview for final eligibility determination, (c) two study visits at which youth will receive TMS or Sham and complete EEG and SST procedures. Assessment procedures include structured diagnostic interviews, and safety screening for TMS. Interested participants will complete a brief phone screen and provide medical records for review before scheduling a clinical interview. Clinical Interview: Participants will complete informed consent (signature required from one parent/guardian), child assent, and assessment of inclusion/exclusion criteria (Mini Kid, CYBOCS, TMS screen; see Measures). Interviews will be administered by the RA, who is already employed at PARC and trained to a reliable standard on all measures. At each of visits 1 and 2, participants will complete a TMS safety screen and medication tracking form; they will then complete the SST with concurrent EEG pre- and post- TMS or Sham. The AEQ will be completed at the end of each visit. Between visits, youth will rate symptoms using EMA (see Measures). Visits 1 and 2 will occur at least one week apart to ensure that any acute TMS effects are no longer active by visit 2. Single session rTMS aftereffects on EEG suggests aftereffect durations <70 min.

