#### Study Design Flow Chart:

#### Study Assessment Measures:

- 1) Mini-Kid; the Mini-Kid 7.0 is a brief, structured interview measuring psychiatric diagnoses in children according to DSM-V and ICD-10 criteria.
- 2) CY-BOCS, is the “gold standard” clinical interview for assessment of OCD symptoms.
- 3) Screening Questionnaire for TMS Candidates; screens for TMS contraindications and will be administered in an interview format with both the child and parent present.
- 4) TMS Adverse Effects Questionnaire (AEQ) is a 13-item questionnaire completed by patient (items 1-10) and clinician (items 11-13).
- 5) The SST is a well-validated computerized task measuring RI. The SST is a visual choice reaction time task in which participants watch arrows (left or right) on the screen and respond by pressing the appropriate button. In a randomly assigned proportion of trials, an audible signal is heard after presentation of the arrow, and subjects are instructed to inhibit the motor response (button press). The inter-stimulus interval and stop-signal delay are varied according to individual performance so that each person can successfully inhibit responses to 50% of stop trials. SSRT (time required to inhibit a prepotent motor response) is calculated from these data. Successful stop trials (i.e., those in which a motor response is successfully inhibited) are most relevant for understanding functional neural correlates of RI, and will be of primary interest in EEG analyses (see below).
- 6) EMA will be used to obtain youth ratings on three items (modified from NIMH rating scales) assessing obsessions, compulsions, and mood on a 7-point scale (1 = not at all to 7 = very much). These items have shown differential change with frequent assessment post-TMS for adults with OCD and have been used in EMA studies of OCD. Youth will receive a text message prompt every two hours (between 9am and 9pm) over the two days following the clinical interview and each study visit (6 days total). The text prompt will include a redcap link for completing EMA items. Similar EMA items and procedures have been used successfully with adolescents of diverse backgrounds in a large number of studies to date.

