#### Description of the Statistical Methods:

Statistical methods align with the Aims of the study, which are as follows:

**Aim 1. Safety and Tolerability.** TMS will be safe and tolerable, as indicated by a comparable rate of side effects associated with TMS vs. Sham (hypothesis 1) and no serious adverse events associated with TMS (hypothesis 2).

**Aim 2. Neural Target Engagement: TMS-induced changes in the RI Network.** Compared with sham, participants will demonstrate significant post-TMS neural changes during SST stop trials, as indicated by increase in frontocentral P3 amplitude

**Aim 3. Behavioral Target Engagement: TMS-induced changes in RI behavior.** Compared with sham, participants will demonstrate a significant post-TMS decrease in SSRT (Hypothesis 1) and EMA-rated compulsions (Hypothesis 2).

**Data Analysis.** We will test **Aim 1 (Safety and Tolerability)** using descriptive data as follows. Hypothesis 1. TMS will be safe and tolerable as shown by total AEQ ratings that are no more than 1 SD higher for TMS vs. Sham (hypothesis 1) and no serious adverse events associated with TMS reported on the AEQ (hypothesis 2). Remaining analyses will use Generalized Linear Mixed Models (GLMM), a variant of Generalized Linear Models (GLM; of which ANOVA, t-test, and regression are special cases) that permit outcome variables with distributions other than Gaussian and additionally permit modeling both fixed and random hierarchical (nested) effects. For each model, the distribution will be selected based on theory (e.g., Poisson for count) and model residuals. **Aim 2 (Neural Target Engagement).** We will examine the significance of TMS-induced neural changes during SST stop trials by testing an interaction between visit type (TMS vs. Sham) and timing of assessment (pre vs. post TMS/Sham) for the the outcome of frontocentral P3 (hypothesis 1). **Aim 3. Behavioral Target Engagement:** We will test an interaction between visit type (TMS vs. Sham) and timing of assessment (pre vs. post TMS/Sham) on RI efficiency as measured by the SSRT (hypothesis 1) and EMA-rated compulsions (hypothesis 2).

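### Aim 1 promises a comparable rate of side effects but is judged on an AEQ total with a 1 SD allowance, which is insensitive to a rise in one or two items

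*Combined protocol and SAP*

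**What the plan says.** In the Description of the Statistical Methods, Aim 1 states that TMS will be safe and tolerable, "as indicated by a comparable rate of side effects associated with TMS vs. Sham". The Data Analysis paragraph then says that Aim 1 will be tested "using descriptive data as follows", and gives the criterion for hypothesis 1: "total AEQ ratings that are no more than 1 SD higher for TMS vs. Sham". The second Aim 1 criterion is that no TMS-associated serious adverse event is reported on the AEQ.

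Study Assessment Measures describes the AEQ as 13 items, ten completed by the patient and three by the clinician. It gives no response scale and no scoring rule. Study Procedures adds: "The AEQ will be completed at the end of each visit". Each participant therefore contributes one AEQ after TMS and one after Sham.

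The plan does not say which SD sets the allowance (Sham, pooled, paired difference or external), or whether group means or within-person values are compared. It contains no proportion of participants with a side effect, no severity threshold and no item-level comparison.

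**The concern.** A rate answers the question of how many participants are affected. A total pools severity, or a count, over all items. If active stimulation adds one or two specific effects, most items in the total do not move, but their person-to-person variation still feeds the SD and so widens the allowance. The criterion can then be met although one non-serious side effect appears after TMS, and not after Sham, in most or all participants. Hypothesis 2 would catch such an effect only if it were serious. At stake is a statement of tolerability in 13- to 18-year-olds that does not answer the aim as worded.

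**Working it through.** **Inputs.** From the documents: the 1 SD criterion, 13 AEQ items, one AEQ per visit, 14 participants enrolled, and 10 in the final sample assumed under Sample size and power. Not in the documents, hence assumed over ranges: item scale, SD of the total, and symptom prevalence under Sham. The plan gives no N, SD, error rate or power for Aim 1, so there is no figure to reproduce.

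**1. What the rule allows.** Let a share q of participants have a new effect scored g points. The mean total rises by q × g. The rule is met if q × g ≤ SD, so the largest share that still passes is min(1, SD/g):

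| SD of total (points) | g = 1 | g = 2 | g = 3 |
|---|---|---|---|
| 0.5 | 50% | 25% | 17% |
| 1 | 100% | 50% | 33% |
| 1.5 | 100% | 75% | 50% |
| 2 | 100% | 100% | 67% |
| 3 | 100% | 100% | 100% |

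**2. What the SD might be.** Take 12 other independent items, each present with probability p under Sham.
- Yes/no items: SD = √(12p(1−p)).
- Items graded evenly 1 to 3 when present (mean 2, mean square 14/3): SD = √(12(14p/3 − 4p²)).

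| p | Yes/no SD | Share passing, g = 1 | Graded SD | Share passing, g = 2 |
|---|---|---|---|---|
| 2% | 0.48 | 48% | 1.05 | 52% |
| 5% | 0.75 | 75% | 1.64 | 82% |
| 10% | 1.04 | 100% | 2.26 | 100% |
| 20% | 1.39 | 100% | 3.05 | 100% |

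Positive correlation between items raises these SDs. A milder severity mix lowers them. With 13 independent items scored 1, 2 or 3 in 60%, 30% and 10% of occurrences, SD = √(13(2.7p − 2.25p²)), which is 0.83 at p = 2% and 1.30 at 5%. A new 2-point symptom in everyone then exceeds the allowance and is flagged; it passes only up to 0.83/2 = 42% and 1.30/2 = 65% of participants.

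**3. Sampling error at N = 10.** The SD would be estimated from few participants, so passing is a matter of chance. I simulated 20,000 trials with 12 background items, a person-level item correlation of 0 to 0.05, and the new effect in all participants after TMS. The probability of passing was:

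| Setting | Sham SD | Pooled SD | Paired-difference SD |
|---|---|---|---|
| Yes/no, p = 10%, g = 1 | 0.50–0.61 | 0.52–0.66 | 0.72–0.77 |
| Yes/no, p = 5%, g = 1 | 0.27–0.38 | 0.23–0.36 | 0.43–0.51 |
| Graded 1–3, p = 10%, g = 1 | 0.81–0.86 | 0.87–0.93 | 0.95–0.96 |
| Graded 1–3, p = 10%, g = 3 | 0.27–0.38 | 0.23–0.36 | 0.47–0.52 |

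The rule often misses a small effect present in everyone, and flags a large one roughly half the time or more.

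**4. Which SD.** For a uniform shift and between-visit correlation ρ of the totals, the SD of paired differences is SD × √(2(1−ρ)). That is 1.41 SD at ρ = 0, 1.00 SD at ρ = 0.5 and 0.63 SD at ρ = 0.8. The undefined SD can therefore make the rule more lenient or stricter.

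**5. What a paired count sees.** A side effect after TMS only in 8 of 10 participants gives an exact McNemar p = 2 × 0.5⁸ = 0.008. In 10 of 10 it is 2 × 0.5¹⁰ = 0.002, and in 14 of 14 it is 0.0001.

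**6. Why no single-item veto.** Suppose there is no TMS effect, p = 10%, and items and visits are independent. The chance that one given item shows an excess of 3 or more participants after TMS is 0.0298 at N = 10 and 0.0545 at N = 14. Over 13 items this becomes 1 − (1 − 0.0298)¹³ ≈ 0.32 and 1 − (1 − 0.0545)¹³ ≈ 0.52. At p = 20% it is 0.65 and 0.80.

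**The case against.** The AEQ's scoring is not visible. The natural reading of a total on a 13-item form is the sum of the items, but the plan does not say so. If items are yes/no, the total is a count of side effects and lies close to a rate. That stands in part: the mismatch then shrinks to pooling over items, but a mean count with a 1 SD allowance still does not show how many participants are affected.

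Aim 1 is also descriptive, in a two-visit study of 14 participants. Serious events have their own criterion, and the HARM form separately assesses suicidal and homicidal ideation. This stands too: there is no error rate to criticise, and safety does not rest on the total alone. Even so, the plan draws a conclusion of tolerability from the rule, and for non-serious effects it is the only criterion.

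A reader might infer that the rule is blind to a single-item effect. The documents do not support that: with rare symptoms under Sham or a large effect, it would often be flagged (steps 2 and 3). Nor can one say that a moderate new symptom in everyone would pass in general; that requires an SD of at least its score, and no SD is given. A reader might also treat the problem as independent of which SD is chosen. Step 4 shows that its size is not.

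**Conclusion.** The point holds in conditional form. Hypothesis 1 is worded as a rate and judged on a pooled total, and no planned analysis counts affected participants. The rule is insensitive, not blind, to a rise in one or two items. A new 1-point effect in every participant meets it if the SD is at least 1 point, and a new 2-point effect if the SD is at least 2. Under the assumptions of step 2, yes/no items reach an SD of 1 at about 10% prevalence per item under Sham, and evenly graded items reach 2 between 5% and 10%. With rarer or mostly mild symptoms the rule is stricter. These figures rest on an additive total, a comparison of group means and an assumed item scale. The wording mismatch itself needs none of these assumptions.

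**What to change.** Keep the AEQ total as a descriptive summary and name the SD reported with it. Judge hypothesis 1 on the rate that it states: the number of participants with at least one AEQ item at or above a severity level fixed before unmasking, TMS visit against Sham visit, as a paired comparison with an exact interval. The investigators should also state, before unmasking, what excess still counts as comparable.

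Add a table of paired counts for each of the 13 items (TMS only, Sham only, both, neither). It should be descriptive, without an automatic veto on any one item, because step 6 shows how often chance alone would trigger one.

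The data are already collected at both visits, so the cost is SAP wording and one table. The downside is a tolerability claim that is harder to meet and an imprecise estimate. Even with no affected participants at a visit, the exact two-sided 95% upper limit for that visit's rate is 1 − 0.025^(1/10) = 31% with 10 participants and 1 − 0.025^(1/14) = 23% with 14. The interval should be reported and the conclusion worded accordingly.

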**7). HARM Form.** At visits 1 and 2, we will administer the HARM form to assess for new or worsening suicidal or homicidal ideation (SI or HI). The Harm Form was developed for SI/HI monitoring by the Child and Adolescent Multimodal treatment Study (CAMS) team^105 and NIMH program staff and was also used in the POTS II and POTS Jr trials for youth with OCD. The form is designed to ascertain the presence of any thoughts, wishes, or behaviors related to self-harm or harm to others since the last study contact. This brief measure consists of two broad initial probes—one asking about self-harm and the other about harm to others—and 5-8 contingent follow-up questions assessing acute risk status.

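### Aim 1's decision rules are narrower than the aim (SAEs counted only if on the end-of-visit AEQ) and declare comparability from a point estimate against an unnamed SD

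*Combined protocol and SAP*

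**What the plan says.** The Aim 1 statement, under Description of the Statistical Methods, says that safety and tolerability will be indicated by a "comparable rate of side effects associated with TMS vs. Sham (hypothesis 1) and no serious adverse events associated with TMS (hypothesis 2". It puts no limit on how a serious adverse event comes to light.

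The Data Analysis paragraph of the same section tests the aim with descriptive data. Hypothesis 1 is met by "total AEQ ratings that are no more than 1 SD higher for TMS vs. Sham". For hypothesis 2 the events are restricted to those on the AEQ, so that the joint criterion reads "no more than 1 SD higher for TMS vs. Sham (hypothesis 1) and no serious adverse events associated with TMS reported on the AEQ". The plan gives no confidence interval, does not say which SD is meant, and states no power or error rate for Aim 1. The sample size paragraph covers Aims 2 and 3 only.

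On collection, Study Procedures says: "The AEQ will be completed at the end of each visit". For the HARM form, Study Assessment Measures says: "At visits 1 and 2, we will administer the HARM form". That form asks about "thoughts, wishes, or behaviors related to self-harm or harm to others since the last study contact" and is not part of the Aim 1 rule. The remaining contact after a visit is two days of text prompts: "EMA will be used to obtain youth ratings on three items (modified from NIMH rating scales) assessing obsessions, compulsions, and mood". Visit 2 is the last visit, and the order of TMS and Sham is randomized.

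**The concern.** Safety is the first aim of a trial in adolescents, and its conclusion follows mechanically from two rules.

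The SAE rule is narrower than the aim it is meant to test. A TMS-associated event in the hours or days after an active visit 2 would contradict the aim, yet hypothesis 2 could still be reported as met under the analysis sentence. After an active visit 1, a later event could at best appear on the visit 2 AEQ, which is the form for the Sham session.

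The AEQ rule treats an observed difference of up to 1 SD as showing comparability. With 10 to 14 participants that difference is imprecise, so a true excess at or above the plan's own margin can be reported as reassuring with no statement of uncertainty. Because the SD is not named, the margin can also be settled after the data are seen.

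**Working it through.** **No figure to reproduce.** Aim 1 has no stated sample size, power or error rate.

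**Inputs.** From the documents: 14 enrolled, each receiving TMS and Sham; N = 10 as the pessimistic final sample for EEG/SST; margin 1 SD. Assumed: normal AEQ totals with equal SD under both conditions, a comparison of group means, and a within-person AEQ correlation r of 0.4 to 0.8. The plan gives .60 to .80 for SSRT and P3, and nothing for the AEQ.

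**1. SAE rule.** Setting the texts side by side:
- Aim: no TMS-associated SAE, any source.
- Analysis: no TMS-associated SAE on the AEQ.
- AEQ timing: end of visits 1 and 2.
- After visit 2, in the visible text: EMA on obsessions, compulsions and mood only.

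With randomized order, about 14/2 = 7 active sessions fall at visit 2 and have no later AEQ or HARM form described.

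Even with full capture, zero events in n sessions has an exact two-sided 95% upper limit of 1 − 0.025^(1/n):
- n = 14: 1 − 0.025^(1/14) = 23%
- n = 10: 1 − 0.025^(1/10) = 31%

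The chance of seeing none is (1 − p)^n. At n = 14 this is 0.95^14 = 49% for a true risk of 5%, and 0.90^14 = 23% for 10%.

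**2. AEQ rule, precision.** In units of the between-participant SD, SE = √(2(1 − r)/N). At N = 14 and r = 0.6, SE = √(0.8/14) = 0.239. The 95% half-width is 2.160 × 0.239 = 0.52. If 1 SD were a known constant, its upper limit would fall below 1 SD only for an observed difference under 1 − 0.52 = 0.48 SD. The plan's rule passes anything up to 1 SD.

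**3. AEQ rule, chance of passing.** For a known SD this is Φ((1 − D)/SE) at true excess D, so exactly 50% at D = 1. The SD has to be estimated, so I simulated it: Sham ~ N(0,1), TMS ~ N(D,1), correlation r; pass if the mean paired difference is at most the sample Sham SD.

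| True excess D | N = 14, r = 0.6 | Range, r 0.4–0.8, N 10 or 14 |
|---|---|---|
| 1.00 SD | 47% | 46–48% |
| 1.25 SD | 19% | 15–25% |
| 1.50 SD | 5% | 2–10% |

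At D = 1 (N = 14, r = 0.6), 42% of trials pass although the 95% upper limit is at or above the margin.

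**4. Which SD.** The SD of paired differences is √(2(1 − r)) times the between-participant SD: 1.10, 0.89 and 0.63 at r = 0.4, 0.6 and 0.8. Share of simulated trials (N = 14) in which two choices give different verdicts:

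| Comparison | D = 0.8 SD | D = 0.3 SD |
|---|---|---|
| Sham SD vs difference SD | 19% (r 0.4), 25% (0.6), 58% (0.8) | 2.5–6% |
| Sham SD vs pooled SD | 8–10% | below 2% |

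**5. Effect of adding the interval.** Share of trials with the 95% upper limit below the Sham SD, r = 0.6:
- No true difference: 94% (N = 14), 82% (N = 10).
- True 0.3 SD excess: 71% and 55%, against 99% and 97% passing the present rule.
- No difference, skewed totals (shared gamma frailty with Poisson counts, mean 0.5–2, shape 0.5–2): 68–92% (N = 14), 56–84% (N = 10).
- True 1 SD excess: about 5%, rather than the nominal 2.5%, because the Sham SD is itself estimated.

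**The case against.** The plan calls Aim 1 descriptive, and descriptive safety reporting is normal with 14 participants. Passing about half the time when the true excess equals the margin is a property of any point-estimate rule, and at 1.5 SD the rule passes only 2–10%. All of this is fair, and the point does not ask for a powered test. What stands is that the text frames these as hypotheses and draws a positive conclusion from a threshold whose SD is not fixed.

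An end-of-visit form is also understandable. The plan puts single-session aftereffects at about 60 minutes (TMS Parameters) and under 70 minutes on EEG (Study Procedures). Those figures concern cortical and EEG effects, and the plan does not use them to set an SAE window.

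Four stronger readings are tempting and not supported:
- **That adverse events after visit 2 are not monitored, or would be discarded.** The flow chart is not shown, other safety procedures may exist outside the visible text, and under the Aim 1 statement itself a known TMS-associated SAE would fail hypothesis 2. The documents show a mismatch between aim and rule, and only suggest a gap in collection.
- **That about 7 of 14 sessions is a rate of missed events.** It counts sessions with no later form described.
- **That the SD choice usually decides the verdict.** The 58% figure is near a worst case: r = 0.8 and a true excess close to the margin. Sham and pooled SD, the more natural readings, seldom disagree.
- **That the AEQ total is undefined.** The AEQ is a cited instrument whose items and scoring may be set out in its source, so silence here is missing detail and not an error.

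**Conclusion.** The concern holds in this form: the Aim 1 rules neither match the aim nor support an unqualified conclusion that TMS is safe and tolerable. The SAE part is textual and needs no assumption beyond the visible text: followed literally, hypothesis 2 could be declared met despite a TMS-associated SAE after an active visit 2. The AEQ part rests on reading the rule as a comparison of mean totals without an interval, on normal totals, and on an assumed correlation; over r = 0.4–0.8 and N = 10 or 14, a true 1 SD excess passes 46–48% of the time. Leaving the SD unnamed matters mainly near the margin and little for small excesses.

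This should be repaired before the data are unmasked. It does not undermine the design, and it does not show that any event would go unrecorded.

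**What to change.** 1. **SAE rule.** Make the analysis match the aim: count TMS-associated SAEs from any source (AEQ, HARM form, spontaneous report) after each session, including visit 2, over a follow-up window that the sponsor sets in advance. To make collection active after visit 2, add one adverse-event item to the last prompt of each existing EMA block. If no SAE is seen, report that with the exact two-sided 95% upper limit (23% at n = 14, 31% at n = 10).
2. **AEQ rule.** Keep Aim 1 descriptive. Fix the SD in advance as the between-participant SD of the Sham totals. Report the paired TMS − Sham difference with its 95% CI beside the 1 SD margin. Where the upper limit reaches 1 SD, say that an excess of that size is not ruled out.

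**Cost.** Wording changes, one item on prompts already scheduled, and staff time to read the answers; no added visits or participants. The real downside is fewer unqualified statements of comparability, as step 5 of the working shows, and more so if AEQ totals are skewed.

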**Study Design:**

We will use a within-subject, counterbalanced design comparing TMS vs Sham in a brief 2-visit protocol enrolling 14 youth (age 13-18) with OCD. At each visit, youth will complete the Stop Signal Task (SST) with concurrent electroencephalogram (EEG) pre- and post- TMS or Sham. TMS will be delivered over pSMA using continuous TBS (cTBS). After each visit, youth will rate symptoms using ecological momentary assessment (EMA).

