#### **Randomization:**

The order in which participants receive TMS and Sham (visit 1 or 2) will be randomly assigned (blocking on medication status, biological sex, and baseline CYBOCS severity) and masked for all study staff except for the statistician.

[figure not shown]

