**Sample size and power.** We anticipate some minimal EEG/SST data loss and participant attrition, very conservatively resulting in a final sample size of  $N = 10$  participants (each with four EEG/SST observations; pre- and post- TMS and Sham). Given this sample size and assuming .80 correlation among repeated measures, power calculations indicate that **Aim 2 and 3** analyses would reach 0.8 power with a medium effect size (Cohen's  $d = 0.51$ ) and alpha = .05. Assuming .60 correlation among repeated measures, analyses would reach .8 power with a medium-large effect size ( $d = .70$ ). Using a TMS protocol similar to that proposed in this application, Obseso (2017) found large effect sizes for cTBS of pSMA on SSRT in healthy adults ( $d = .95$ ). Available data for proposed outcome variables suggest that repeated measures correlations will fall between .60 and .80, with SSRT showing correlations between .65-.73 and P3 showing correlations of .68-.71.

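### The two-visit crossover models for P3, SSRT and EMA compulsions pre-specify no visit-number term, and EMA has no visit-specific baseline

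*Combined protocol and SAP*

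**What the plan says.** Study Design describes a "within-subject, counterbalanced design comparing TMS vs Sham in a brief 2-visit protocol". Under Randomization the order is random, "blocking on medication status, biological sex, and baseline CYBOCS severity"; no ratio between the two orders is given.

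Under Description of the Statistical Methods, the Aim 2 analysis of P3 is "testing an interaction between visit type (TMS vs. Sham) and timing of assessment (pre vs. post TMS/Sham"). Aim 3 applies the same interaction "on RI efficiency as measured by the SSRT (hypothesis 1) and EMA-rated compulsions (hypothesis 2"). The model class is a GLMM that can hold fixed and random effects. No section names visit number, period or order as a term.

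The sample-size paragraph allows for data loss and attrition, "very conservatively resulting in a final sample size of" 10 out of 14, "each with four EEG/SST observations; pre- and post- TMS and Sham". It does not discuss how those 10 divide by order.

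EMA follows a different schedule. In Study Assessment Measures, item 6, ratings are collected "over the two days following the clinical interview and each study visit (6 days total"). That gives one window before any stimulation and one after each visit. The plan does not say how the single early window acts as pre for two visits.

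**The concern.** In a two-visit crossover each participant's TMS-minus-Sham contrast is also a visit 1-minus-visit 2 contrast, with a sign set by the order received. Random order balances this in expectation. It does not balance it in the sample analysed if the two orders lose different numbers of participants.

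A visit effect is plausible here. The stop-signal task is given four times, so early practice may affect the first visit's pre-post change more than the second's. Motor threshold is determined at the first visit only. The gap of at least one week in Study Procedures is aimed at acute carryover and does not deal with visit effects.

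At stake is an estimate that depends partly on who was lost. When the orders are even, the cost is instead an error term enlarged by the unmodelled visit difference. EMA compulsions are the most exposed outcome because they have no baseline of their own at each visit.

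**Working it through.** **The plan's own figure.** The stated d = 0.51 (correlation .80) and d = 0.70 (correlation .60) at N = 10 are reproduced approximately by a four-measurement repeated-measures F test on 3 and 27 df. With lambda = (d/2)^2 x N x 4/(1-rho), power is 0.813 and 0.787. That calculation has no visit effect in it. The power figures below instead use the single-df interaction contrast, so they are not comparable with the plan's 0.8.

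**P3 and SSRT.** Let tau be the TMS effect on pre-post change, D the visit 1-minus-visit 2 difference in pre-post change, and n1 and n2 the completers with TMS first and Sham first.
- TMS-first contrast: tau + D. Sham-first contrast: tau - D.
- Mean over N = n1 + n2: tau + D x (n1-n2)/N.
- A plain visit shift adds equally to pre and post within a visit, so it drops out.

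**EMA.** With interview-window mean B used as pre for both visits, the contrast is (post-TMS - B) - (post-Sham - B) = post-TMS - post-Sham. B drops out, and a plain visit shift L takes the place of D. A visit-number main effect moves pre and post together, so it leaves the interaction unchanged. With L = 0.5 SD the movement is 0.10 SD at 6:4 and 0.20 SD at 7:3, with or without that main effect. It is zero once visit number x timing is included.

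**How often the split is uneven.** Assume 7:7 at the start (inferred from the counterbalancing) and loss unrelated to order, so the split is hypergeometric.
- Ten completers: 5:5 0.44, 6:4 0.49, 7:3 0.07. Uneven: 0.49 + 0.07 = 0.56.
- Twelve completers: 6:6 0.54, 7:5 0.46.

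**Size of the movement**, for an assumed D or L of 0.25 to 0.5 SD:
- 6:4: 0.2 x 0.25 = 0.05 to 0.2 x 0.5 = 0.10 SD.
- 7:3: 0.4 x 0.25 = 0.10 to 0.4 x 0.5 = 0.20 SD.
- 7:5: (2/12) x 0.25 = 0.04 to (2/12) x 0.5 = 0.08 SD.
- Average absolute movement over splits at N = 10: 0.03 to 0.06 SD. Average signed movement: zero.

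**Type I error without the term**, nominal 0.05, D or L = 0.5 SD, N = 10, rho .70. P3/SSRT: 0.033 at 5:5, 0.038 at 6:4, 0.059 at 7:3. Over the correlations and both outcomes examined, the highest value is 0.064, at 7:3. With the term it is 0.049-0.050.

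**Power, two-sided 0.05, without vs with the visit terms**, averaged over splits and both directions. P3/SSRT: one contrast per person with variance 4(1-rho), rho .70, d .95 (the healthy-adult SSRT effect cited in the plan, taken here as the difference in pre-post change). EMA: direct comparison with variance 2(1-rho), one mean score per window; its d .70, rho .70 and N = 10 are all assumed.

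| Outcome, N | D or L = 0 | 0.25 SD | 0.5 SD |
|---|---|---|---|
| P3/SSRT, 10 | 0.685 vs 0.657 | 0.664 vs 0.658 | 0.604 vs 0.659 |
| P3/SSRT, 12 | 0.781 vs 0.767 | 0.764 vs 0.768 | 0.709 vs 0.767 |
| EMA direct, 10 | 0.721 vs 0.693 | 0.680 vs 0.693 | 0.569 vs 0.694 |

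Power with the terms does not depend on D or L; the third-decimal differences along a row are simulation noise. For P3/SSRT at N = 10 the break-even is near D = 0.3 SD. At D = 0 / 0.25 / 0.5, rho .60 gives 0.563 vs 0.537, 0.546 vs 0.538 and 0.500 vs 0.538; rho .80 gives 0.846 vs 0.823, 0.825 vs 0.824 and 0.750 vs 0.824.

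**The case against.** Several points on the other side stand.

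- Random order makes the estimate unbiased over randomisations when loss is unrelated to order. The movement described here is conditional on the split obtained, and the 7:3 case has probability only 0.07.
- The documents give no D or L. For P3 and SSRT at N = 10 the added terms lose power at D = 0, lose a little at 0.25 SD and clearly gain only at 0.5 SD, which is about the plan's own detectable effect of 0.51. That D would have to be a difference in pre-post change, not ordinary practice between visits.
- The statistical section names the interaction to be tested, not a full covariate list, and a GLMM could hold a visit term. The fair criticism is that the term is not pre-specified, not that it is excluded.
- N = 10 comes from EEG/SST loss and attrition together. EEG/SST loss does not remove EMA ratings, so EMA may have more completers.

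Two stronger readings are not supported. A reader might infer that the planned TMS contrast is biased outright or that its type I error is seriously inflated. The average movement is zero and the error rate reaches about 0.06 at worst in the cases examined. A reader might also infer that reusing the interview window makes the EMA test conservative. With prompts scheduled as "Youth will receive a text message prompt every two hours (between 9am and 9pm") there are 7 a day and 14 per two-day window. A random-intercept model at prompt level then has size from below 0.01 to about 0.19 as the assumed window-level share of within-person variance goes from 0% to 23%. The direction is therefore not settled by the documents, and reuse of the window is itself a supposition.

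**Conclusion.** The point holds as a cheap improvement of modest priority. No visit-number term is pre-specified for a two-visit crossover, and the EMA test as worded has no visit-specific pre measurement. On the plan's N = 10 and an assumed 7:7 start, an uneven split is more likely than not (0.56). The estimate then moves by 0.05-0.10 SD at 6:4 and 0.10-0.20 SD at 7:3 for an assumed visit effect of 0.25-0.5 SD, in either direction. The main gain is an estimate that does not depend on which participants are lost. A power gain for P3 and SSRT at N = 10 needs D above about 0.3 SD. The EMA part is the firmer one: which window is pre has to be settled whatever the size of any visit effect. The power figures use one contrast per person, a simplification of the planned GLMM.

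**What to change.** 1. In the P3 and SSRT models, pre-specify visit number and visit number x timing as fixed effects alongside visit type x timing.
2. For EMA compulsions, compare post-TMS with post-Sham ratings directly, with visit number as a fixed effect. If visit type x timing is kept, include visit number x timing and state which window is pre for each visit; a visit-number main effect alone does not remove the movement. The interview-window rating is constant within a person, so adding it as a covariate cannot do this job when both visits are observed.
3. In either EMA model, allow for correlation of prompts within a window, for example with a window-level random effect.

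The cost is analysis wording, with no new data or visits. Residual df for the contrast fall from 9 to 8 at N = 10, and the standard error is multiplied by 1/sqrt(1-((n1-n2)/N)^2): 1.00 at 5:5, 1.02 at 6:4, 1.09 at 7:3. With no visit effect, average power at N = 10 falls by about 0.03: P3/SSRT from 0.685 to 0.657 (0.670, 0.654 and 0.598 at the three splits), and direct EMA from 0.721 to 0.693 (0.707, 0.690 and 0.632). At N = 12 the average loss is about 0.014.
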